#### **Treatment (over the course of 4-6 weeks, 1 hour sessions, up to 3 sessions/week)**

- During treatment clinic visits, participants who are randomized into the **active taVNS + exercise** group will receive 15 minutes of active taVNS prior to treatment.
- Participants who are randomized into the **non-active taVNS + exercise** group will receive 0 mA of current for 15 minutes prior to treatment.
- To implement the non-active condition, participants will still undergo the same electrode placement procedure as those in the active taVNS group, with the electrodes placed in the ears. However, the taVNS device will be set to a 0 mA (no stimulation) during the non-active condition. Participants will be informed prior to the stimulation that they may or may not feel anything during the session, and that just because they do not feel anything does not mean that they are not receiving stimulation.

- All participants will be guided through low intensity, high amplitude exercises led by a trained exercise specialist.
- The exercise intervention proposed involves the supervision of a trained exercise specialist at all times during the treatment session
- The use of a gait belt will further ensure the participant's safety by providing additional support and stability during exercise
- The proposed exercise intervention will be conducted by a trained exercise specialist who has expertise in assessing and managing potential risks associated with exercise interventions. This will ensure that the intervention is safe for the participant and will minimize the risk of injury or adverse events
- After each treatment session, participants will be asked post-intervention questions to evaluate potential side effects of the taVNS treatment and exercise (see below):
  - 1. Since our last session, have you experienced any unusual physical symptoms such as dizziness, fatigue, muscle soreness, shortness of breath, or heart palpitations?
  - 2. Have you experienced any unusual discomfort or pain in the ear where the taVNS device was applied?
  - 3. Have you noticed any changes in your skin around the area where the taVNS device was applied, such as redness, swelling, or rash?
  - 4. Have you felt any changes in your mood, like feeling more anxious, depressed, or irritable since the last session?
  - 5. Have you noticed any changes in your ability to concentrate or remember things?

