  - 6. Have you experienced any other side effects or symptoms that you believe may be related to the taVNS treatment or exercise program?
- If a participant reports experiencing any adverse effects, they will be advised to seek appropriate medical attention. We will also document all reported side effects.
- Participants will wear a heart rate monitor during each treatment session to monitor and record heart rate response to exercise.
- Participants will be asked to answer a series of questions about the tolerability of the taVNS treatment & exercise intervention via a RedCap survey.

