**Statistical Analysis:**

To assess feasibility, we will track recruitment rate, retention rate, adverse events, and compliance. We will obtain patient feedback to gather insight about the acceptability and usability of this intervention. We will perform paired t-tests to compare the mean outcome measure values of the treatment and control groups to estimate effect size.

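### Post-session question 5 does not separate better from worse concentration or memory, and question 1 does not require a record of which symptom occurred

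*Combined protocol and SAP*

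**What the plan says.** The Treatment section states that after each session "participants will be asked post-intervention questions to evaluate potential side effects of the taVNS treatment and exercise". Six questions follow.

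- Question 1: "have you experienced any unusual physical symptoms such as dizziness, fatigue, muscle soreness, shortness of breath, or heart palpitations", asked for the time since the last session.
- Question 2: "Have you experienced any unusual discomfort or pain in the ear where the taVNS device was applied".
- Question 3: skin changes near the device, with harmful examples.
- Question 4: "Have you felt any changes in your mood, like feeling more anxious, depressed, or irritable since the last session".
- Question 5: "Have you noticed any changes in your ability to concentrate or remember things".
- Question 6: "any other side effects or symptoms that you believe may be related to the taVNS treatment or exercise program".

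On handling the answers, the section says that a participant who reports an adverse effect is advised to seek medical attention, and then: "We will also document all reported side effects". The Statistical Analysis section adds: "To assess feasibility, we will track recruitment rate, retention rate, adverse events, and compliance". It then describes a comparison of outcome measure values between the treatment and control groups.

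**The concern.** A list meant to find harm should be answerable only by harm, or should at least record direction. Question 5 does neither. A participant whose concentration has improved would truthfully say yes. Attention and memory are also measured as outcomes, so the same change could appear as a gain on the cognitive tests and as an entry among the side effects. With no recall period, a single lasting change could also be reported session after session.

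Question 1 has a different weakness. It offers five symptoms in one item and does not require the form to show which one occurred or when it began.

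At stake is how well the adverse-event summary can be read. In a study of up to 20 people, a few ambiguous answers can alter that summary, and neither direction nor symptom can be reliably recovered later if it was not written down at the session.

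**Working it through.** The plan states no adverse-event rate, power or derived sample size, so there is no figure to reproduce. The check is mainly a comparison of texts.

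**1. The six items side by side**

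| Question | Signals harm? | Recall period? | Separates stimulation from exercise? |
|---|---|---|---|
| 1 | Yes, five symptoms in one item | Since last session | No |
| 2 | Yes | None | Device site only |
| 3 | Asks about changes; examples are harmful | None | Device site only |
| 4 | Asks about changes; examples are worsening | Since last session | No |
| 5 | No | None | No |
| 6 | Yes | None | No, joins the two |

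Questions 3, 4 and 5 all ask about changes. Question 5 is the only one with nothing in its wording that points to harm. It is not alone in lacking a recall period, but it matters more there because a cognitive change can persist.

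**2. Overlap with the outcomes.** Under Cognitive Assessments, Digit Span measures working memory, the Flanker and Digit Symbol tests measure attention, and the MoCA covers both domains. Under Questionnaires, NeuroQOL asks participants about their own memory and attention. All are repeated at Re-Assessment and Follow-up. Question 5 therefore covers the same ground as several outcome measures.

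**3. Does another section repair it?** The Treatment section promises to document side effects, but gives no direction follow-up, severity grade, attribution step or coding rule. The REDCap tolerability survey (Treatment and Re-Assessment) is mentioned without its content. The tolerability interview takes place only at Re-Assessment. The Statistical Analysis section tracks adverse events without defining how answers become events.

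**4. How often the form is used.** Inputs: 4 to 6 weeks and up to 3 sessions a week (Treatment); up to 20 participants (Patient Population).

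- Sessions per participant: 3 × 4 = 12 to 3 × 6 = 18, at most.
- Administrations: 12 × 20 = 240 to 18 × 20 = 360, at most.
- One lasting change, noticed from the first session, could be reported at most 12 to 18 times.

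**5. Illustration with assumed rates.** Let *p* be the chance per session of a yes to question 5 that reflects improvement or noise, independent between sessions. The chance of at least one such yes over *n* sessions is 1 − (1 − *p*)^*n*.

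| Assumed *p* | *n* = 12 | *n* = 18 | Expected participants of 20 |
|---|---|---|---|
| 2% | 21.5% | 30.5% | 4.3 to 6.1 |
| 5% | 46.0% | 60.3% | 9.2 to 12.1 |
| 10% | 71.8% | 85.0% | 14.4 to 17.0 |

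The documents give no value for *p*. The table shows only that an undirected item asked this often will collect some yes answers that are not harms.

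**6. Question 1.** Let *b* be the chance of a yes for any reason common to both arms, and *s* the chance that stimulation adds a symptom, independently. The control arm answers yes with probability *b*, and the active arm with 1 − (1 − *b*)(1 − *s*) = *b* + *s*(1 − *b*). The difference is *s*(1 − *b*). A higher background shrinks it, but it does not vanish unless *b* = 1. The background for any one symptom cannot exceed the background for all five together, so recording symptoms separately reduces the dilution.

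**The case against.** The strongest reply is that the harm depends on a scoring rule that the documents do not contain. Nothing says the answers are yes/no ticks, that they are totalled by item, or that a yes to question 5 becomes an adverse event. What is to be documented is the side effect reported, and better concentration is not one in ordinary usage. The item also sits in a list introduced as being about side effects. Staff may well ask which way the change went, and a participant answering question 1 may simply name the symptom. This stands, and it makes the problem a possibility the plan leaves open, not a certainty.

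Three stronger readings are tempting, and the documents do not support them.

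- *A reader might infer that adverse-event counts are biased against active stimulation.* The Statistical Analysis section tracks adverse events for feasibility and commits to no comparison of them by arm. Nor does the plan state a cognitive hypothesis or a primary outcome. The Flanker and SF-36 descriptions tie their results to the effectiveness of the exercise intervention, which both arms receive.
- *A reader might infer that question 1 hides an effect of stimulation.* Both arms exercise and have the same electrode placement, so a group excess could still show. Pooling weakens it without removing it.
- *A reader might sort the question 1 symptoms into those due to stimulation and those due to exercise.* No section makes that allocation.

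It is also fair to say that questions 2 and 3 are specific to the device site, and that the survey and interview give other routes to tolerability information. They limit the damage. They are not described as recording direction or onset at each session, so they do not close the gap.

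**Conclusion.** The point holds as a minor weakness in data collection. Question 5 lacks a direction and a recall period in a domain that is also an outcome. An improvement could therefore be recorded as a side effect, and a lasting change reported repeatedly, unless staff ask further. Question 1 loses the identity and timing of symptoms unless someone chooses to note them.

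The conclusion rests on the printed questions being what participants are asked and on no unpublished form supplying the missing detail. The size of the effect on the adverse-event summary cannot be estimated from the documents. The figure of 12 to 18 reports per participant is a ceiling on repetition, not a measure of error, and the conclusion does not depend on the assumed rates. The comparison of outcome measures and the sample size are unaffected.

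**What to change.** - Reword question 5 along these lines: *Since the last session, has your concentration or memory become better, become worse, or not changed?* Count only a worse answer as a possible side effect. The first session has no earlier one to refer to, so state a reference point for it, such as the initial assessment.
- Give each symptom in question 1 its own line, with the time it began.
- State in the Statistical Analysis section that answers to both questions will be summarised by arm.

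The cost is an edit to the session form and about a minute more per session. It needs no extra visits or staff.

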**Inclusion Criteria:**

1. 1. Diagnosis of Parkinson's Disease by a board-certified Neurologist, or by a Nurse Practitioner or Physician Assistant under the supervision of a Neurologist.
2. 2. Age between 35 and 80 years
3. 3. No walking aids
4. 4. Stable medication 4 weeks prior to the study
5. 5. No falls in the past 6 weeks
6. 6. Must have a neurologist or movement disorder specialist willing to approve and monitor their participation in the 'off' state' period of the study\*\*

**\*\*Clinically Defined "Off" State:** Patients with Parkinson's disease have motor and cognitive fluctuations that can impact the interpretation of assessments performed in different medication states. To address this, we will conduct the initial evaluation in the practically defined off medication state, defined as when the participants have refrained from taking their PD medications for a period exceeding 12 hours. In this off medication state, we aim to observe and measure changes in the cardinal PD symptoms: tremor, rigidity, bradykinesia, and dyskinesias. These observations will be made using the physical and cognitive assessments described below. This approach is vital to our study as it allows us to investigate the effects of the intervention in isolation. To mitigate any potential discomfort or adverse effects, this will be done under the careful supervision of our clinical team, which is supervised by [name], who is a neurologist specializing in the treatment of individuals with Parkinson's Disease. Additionally, we will obtain consent from the participants provider to ensure that they are safe to withhold PD medications for 12 hours prior to enrolling the participant in our study. *To further ensure participant safety, we will require that the participant has someone drive them to and from their clinic visits when they are in the clinically defined off state.* We will ensure participant safety and comfort throughout the evaluation sessions, intervening immediately if any adverse effects are observed. By focusing on the clinically defined 'off' medication state, we hope to gain a clearer understanding of the standalone effects of the brain stimulator on the symptoms and progression of Parkinson's disease. The findings of this study may contribute to future developments in the management and treatment of this debilitating condition.

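### Out-of-session falls and other non-symptom events that the participant thinks unrelated are not systematically asked about, so the adverse-event measure may under-count them

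*Combined protocol and SAP*

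**What the plan says.** The Statistical Analysis section makes adverse events one of four feasibility measures: "To assess feasibility, we will track recruitment rate, retention rate, adverse events, and compliance". It does not define an adverse event or say which sources feed the count.

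The only repeated safety enquiry whose content is given is in the Treatment section: "After each treatment session, participants will be asked post-intervention questions to evaluate potential side effects of the taVNS treatment and exercise". Six questions follow. Question 1 asks: "Since our last session, have you experienced any unusual physical symptoms such as dizziness, fatigue, muscle soreness, shortness of breath, or heart palpitations". Questions 2 and 3 concern ear discomfort and skin changes at the device site. Question 4 concerns mood ("Have you felt any changes in your mood, like feeling more anxious, depressed, or irritable since the last session") and question 5 cognition ("Have you noticed any changes in your ability to concentrate or remember things"). Question 6 is the closing catch-all: "Have you experienced any other side effects or symptoms that you believe may be related to the taVNS treatment or exercise program". On recording, the section says: "We will also document all reported side effects".

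Falls appear elsewhere in the document only in an inclusion criterion ("No falls in the past 6 weeks") and in the description of the Functional Gait Assessment, which is said to address the risk of falling.

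**The concern.** A catch-all safety item should pick up whatever the specific items miss. Question 6 narrows what it can pick up in two ways. It asks for symptoms or side effects, and a fall without lasting symptoms, a minor injury or an unplanned medical visit is not naturally described as either. It also asks the participant to decide on causation before answering, so an event blamed on something else need not be mentioned.

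The omission of falls stands out because the plan itself treats them as relevant. It requires a fall-free period before entry, uses a gait belt during exercise, and measures balance and gait with several instruments. Yet no listed item asks whether a fall happened during the trial. At stake is the completeness of a named feasibility measure. With up to 20 participants, one or two unrecorded events would noticeably change the safety picture that a later, larger trial would rely on.

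**Working it through.** The documents give no adverse-event rate or fall rate, so there is no figure to reproduce. The check is a reading of the six items against the kinds of event that could occur.

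**Step 1: the items side by side.**

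| Item | Domain | Needs the participant to believe it related? | Names falls, injuries or medical visits? |
|---|---|---|---|
| 1 | Unusual physical symptoms, with examples | No | No |
| 2 | Ear pain or discomfort | No | No |
| 3 | Skin at the device site | No | No |
| 4 | Mood | No | No |
| 5 | Concentration and memory | No | No |
| 6 | Any other side effect or symptom | Yes | No |

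One of six items carries an attribution condition, and it is the catch-all. None of the six names a fall, injury or medical visit.

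**Step 2: trace each kind of event.**

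- *Fall or injury during a session:* a trained specialist is present throughout, so it would be seen.
- *Event outside a session that causes physical symptoms:* question 1 is open-ended within physical symptoms and has no attribution condition, so it can be reported there whatever the participant blames.
- *Event outside a session, without symptoms, thought related to taVNS or exercise:* may be reported under question 6.
- *Event outside a session, without symptoms, thought unrelated:* no described item prompts it. Capture depends on the participant volunteering it, or on the tolerability survey or interview, whose questions are not given.

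The last category is the gap.

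**Step 3: how much of the week is unobserved.** Sessions last 1 hour, with up to 3 a week, so supervised time is at most 3 × 1 = 3 hours of 7 × 24 = 168, or 3/168 = 1.8%. This describes hours, not risk; an hour of exercise may carry more risk than an ordinary hour. It shows only that supervision cannot stand in for asking about the rest of the week.

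**Step 4: can the under-count be sized?** Suppose, as a limiting case, that question 6 were the only route by which an out-of-session fall is recorded, and let *a* be the share of such falls that participants believe related. The share missed is 1 − *a*. The documents say nothing about *a*, so the result can lie anywhere from 0% (*a* = 1) to 100% (*a* = 0). Other routes exist, so the true share missed would be no larger than 1 − *a*. No useful magnitude follows.

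**Step 5: the later visits.** The questions are tied to treatment sessions. The Re-Assessment section adds a tolerability interview and survey but does not list the six questions. The Follow-up section lists no safety questions. Events after the last treatment session therefore have no described safety prompt beyond the tolerability enquiry at re-assessment.

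**The case against.** The strongest reply is that question 6 does not decide what is counted. Nothing in the plan limits the adverse-event count to question 6, or to the questionnaire at all, and the promise to document reported side effects carries no relatedness condition. Question 1 is broad and unconditional, sessions are supervised throughout, staff watch for adverse effects at evaluation visits, and there is a tolerability survey and an interview. All of this stands, and it narrows the point to the last category in the tracing above. It does not close it: supervision covers little of the week, the survey and interview are described only as addressing tolerability or feasibility, and volunteered reports are not systematic enquiry.

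A reader might also infer that belief about relatedness will differ by arm, because the control arm receives 0 mA and every eligible participant has a short tolerance trial of taVNS beforehand, so that the arms' adverse-event rates would be distorted. The documents do not support taking it that far. Question 6 covers the exercise as well as taVNS, and both arms exercise. Participants are told that feeling nothing does not mean they are not being stimulated. The analysis section states no between-arm comparison of adverse events; its t-tests concern outcome measure values. Differential attribution is conceivable, but its direction and size would rest wholly on assumption.

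**Conclusion.** The point holds in a limited form. Out-of-session falls and other non-symptom events that the participant thinks unrelated are not systematically elicited, and may be under-counted in a named feasibility measure. A reader might infer that such events drop out of the count altogether; the text does not say so, because it does not define the count and leaves other routes open. The size of any under-count cannot be derived from the documents. The conclusion assumes only that the questions are put as written and that the unseen survey and interview questions are not relied on to ask about falls. It is a cheap improvement to data capture and does not threaten the design.

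**What to change.** 1. Reword question 6 so that it does not depend on attribution, for example: *Have you had any other new symptom, injury, fall, illness or medical visit since we last asked, whether or not you think it is related to the study?*
2. Add a separate yes/no item on falls since the last contact.
3. Ask the same items at re-assessment and follow-up.
4. Have the investigator record relatedness afterwards, as a classification of a recorded event and not a condition for recording it.

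A sentence in the Statistical Analysis section defining an adverse event and naming the sources that feed the count would complete the change.

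The cost is one reworded question, one added item and its use at two further visits. The raw event count will be somewhat higher and there will be slightly more review work. Recording relatedness separately lets related events still be reported on their own.

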### Re-Assessment (2 hours)

\*\*Prior to the re-assessment, enrolled participants will receive an email from the study coordinator outlining the requirements of the clinically defined "off" state.

- All participants will complete outcome measure assessment after completion of the protocol, including re-administration of the Montreal Cognitive Assessment (**MoCA**), Movement Disorder Society-Sponsored Revision of the Unified Parkinson's Disease Rating Scale(**MDS-UPDRS**), 6-minute walk test (**6MWT**), mini-Balance Evaluation Systems Test (**Mini-BESTest**), Functional Gait Assessment (**FGA**), the modified Clinical Test of Sensory Integration and Balance (**mCTSIB**), Delis-Kaplan Executive Functioning System (**DKEFS**), Digit span test (DST), Digit symbol substitution test (DSST), Flanker test, **PROMIS-NeuroQOL**, the Short Form-36 (**SF-36**)
- Additionally, participants will complete a qualitative interview to assess tolerability and feasibility of the treatment provided in this study. The interview will be recorded and transcribed on a HIPPA compliant platform and will be stored in a secure database. Audio and transcription will be analyzed at the conclusion of the study.
- Participants will be asked to answer a series of questions about the tolerability of the taVNS treatment & exercise intervention via a RedCap survey.

*Participants will be compensated with a \$100 clincard at the conclusion of this visit.*

